Outcomes: Images will be evaluated qualitatively and quantitatively. Data will be submitted to Avid for qualitative analysis. Images will be visually examined by a trained radiologist or nuclear medicine physician who is blinded to the subject diagnosis and will be reported as either A β elevated (AD-like) or A β non-elevated (not AD-like). Qualitative interpretation will be performed in the following manner: the images will be reviewed using a black-white scale with maximum intensity of the scale set to the maximum intensity of all brain pixels. A elevated scan will have at least one area where the grey matter is more intense than adjacent white matter or at least 2 brain areas where the grey white contrast is reduced or absent. For quantitative evaluation, standard uptake values (SUV) will be calculated using SPM software in 6 cortical areas (frontal cortex, temporal cortex, parietal cortex, precuneus, anterior and posterior cingulate) and the cerebellum. SUV ratios (SUVR) for cortical target areas relative to the cerebellum will also be calculated and a global mean SUVR will be calculated from the average across all cortical target areas.

Statistical Analyses for Aim 1: This is a two-arm, 2:1 randomized, controlled clinical trial comparing 52 weeks of aerobic exercise to control intervention. Based on drop out rates from those who have completed our exercise trials (2 of 53 [4%] dropped out of the TEAM study and 1 of 11 [9%] dropped out of ADEPT), we conservatively estimate that 15% of the subjects will drop out of the study, leaving approximately 85 subjects for analysis. We will perform analyses based on intent-to-treat to maintain the benefits of the randomization. Per protocol analyses will also be conducted among the subjects that complete a minimum of 80% of their sessions. To further assess the response to aerobic exercise, we will conduct analyses that replace the primary explanatory factor (treatment group) with continuous measures of increase (change from baseline) in aerobic fitness (VO₂peak). This will allow us to assess the aerobic fitness hypothesis which states that aerobic fitness gains mediate neural benefits of exercise.

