We hypothesize that 52 weeks of aerobic exercise will lower amyloid burden as measured by Florbetapir PET imaging. Amyloid burden will be measured at baseline and at 52 weeks as a ratio of standard uptake values in six regions of interest to the cerebellum. Our primary amyloid burden outcome measure will be the 52-week change in Florbetapir cortical-to-cerebellar ratio averaged across these six regions of interest. The primary intent-to-treat analysis for amyloid burden will compare the change from baseline to 52 weeks between our two treatment groups using the two-sample t-test. Similar analyses will be conducted for each of the ratios for the six regions of interest individually (secondary measures), and for per-protocol analyses described above. Given the single primary measure for this aim, no multiplicity adjustment will be made and secondary endpoints will be clearly indicated as such in resulting manuscripts. To evaluate the appropriateness of our

approach (two-sample t-test), residual analysis will be conducted. This will include visual inspection of the residuals and comparison of the estimated standard deviation across groups to assess homogeneity of variances. If these diagnostics indicate concerns with our parametric approach, appropriate alternative strategies, such as nonparametric methods like the Wilcoxon rank-sum test or data transformation, will be utilized. Ordinary least squares (OLS) regression models will be used for the per protocol analyses that will assess increase in aerobic fitness as continuous measures with amyloid burden outcomes. Model assessment for these OLS models will also be conducted by assessing model assumptions through residual analyses (e.g., predicted versus residual plots, quantile-quantile [q-q] plots, etc.).

Aim 2: Determine if aerobic exercise attenuates structural brain changes in preclinical AD and those without elevated amyloid.

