We have identified primary endpoints for intent-to-treat analyses between treatment groups within each study aim: change in amyloid burden (Aim 1); hippocampal atrophy (Aim 2); and change in executive function (Aim 3). Other endpoints and analyses will be described in resulting publications as secondary. For all analyses the traditional type I error rate of $\alpha=0.05$ will be used. We will use two-sided tests to further protect against spurious results. Our primary intent-to-treat analyses will be based on the two-sample t-test. **Table 2** presents the power for each aim of our study corresponding to our primary measures. Anticipated effect sizes are presented using Cohen’s d (expected average group difference divided by the assumed, common standard deviation). We assumed 15% of our 100 enrolled subjects will be lost to attrition, so power calculations assumed 56 subjects in our exercise intervention arm and 28 subjects in our control group.

Table 2. Anticipated study power

Study aim	Primary measure*	Effect size (Cohen’s d)	Power
Aim 1	Amyloid burden	0.79	92.9%
Aim 2	Hippocampal volume	0.66	81.4%
Aim 3	Executive function	2.32	>95%

*Primary measures are change from baseline to 52-week follow-up.

Aim 1: A 78 week study assessing Bapineuzumab¹¹⁹ in AD demonstrated a mean change in cortical PIB retention (average across six cortical regions) of -0.09 (0.16 SD) for those treated with Bapineuzumab (n=20) and 0.20 (0.09) for those on placebo (n=7). Given the differences in our proposed study (preclinical AD sample, lower expected amyloid burden, shorter duration) we determined power allowing exercise to have a lower effect size. An effect size only 40% as large will produce a Cohen’s d of 0.79. Thus, Aim 1 will have 93% power to detect this conservative anticipated effect of exercise on amyloid burden (and 81.9% power to detect 30% of the Bapineuzumab effect size).

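### Regressing outcome change on VO2peak change, with treatment group removed, cannot assess whether fitness gains mediate the benefit of exercise; report it as a non-randomised association

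*Combined protocol and SAP*

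**What the plan says.** The primary Aim 1 outcome is "the 52-week change in Florbetapir cortical-to-cerebellar ratio averaged across these six regions of interest", compared between arms by a two-sample t-test under intention to treat.

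Statistical Analyses for Aim 1 then adds analyses that "replace the primary explanatory factor (treatment group) with continuous measures of increase (change from baseline) in aerobic fitness" (VO2peak). The purpose is stated directly: "This will allow us to assess the aerobic fitness hypothesis which states that aerobic fitness gains mediate neural benefits of exercise".

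The model is specified in the next paragraph of that section: "Ordinary least squares (OLS) regression models will be used for the per protocol analyses that will assess increase in aerobic fitness as continuous measures". No arm term, covariate, indirect-effect estimate or causal caveat is given for VO2peak.

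Three other places bear on this:
- Statistical Analyses for Aim 3 sets out a stepwise mediation procedure, but the mediator there is hippocampal atrophy. That section also examines exercise through the continuous measure carried over from Aim 1.
- Sample Size Justification makes all analyses other than the three primary comparisons secondary.
- Preliminary Experience under Aim 2 reports that decline in fitness goes with greater parahippocampal atrophy, and acknowledges that those data do not come from an exercise intervention.

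**The concern.** Change in VO2peak is measured after randomisation. Intercurrent illness, general health and test effort can move both it and the brain or cognitive outcome over the same 52 weeks. Once arm is removed, the slope mixes three things: an effect through fitness, an effect of exercise by other routes, and shared causes unrelated to exercise. A significant slope does not say which of these is present.

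The plan nevertheless commits in advance to reading that slope as evidence on mediation. A trial whose randomised comparison is null could therefore report support for the aerobic fitness hypothesis. A trial in which exercise works by some other route could credit fitness.

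**Working it through.** **Inputs from the documents.** Two-sided alpha 0.05; 56 exercise and 28 control (n = 84); Aim 1 d = 0.79 (Sample Size Justification). TEAM six-month VO2peak changes: −1.1 ml/kg/min without exercise and +1.5 at the 100% dose, a gap of 1.5 − (−1.1) = 2.6 (KU ADC Exercise Trial Experience).

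**Assumptions.** The documents give neither the SD of VO2peak change nor its within-arm correlation r with outcome change. I take SD 2 to 4, so the arm gap g runs from 2.6/4 = 0.65 to 2.6/2 = 1.3 SD, with g = 1 as the central case. I take r from 0 to 0.3.

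**Step 1. The plan's own figure.** √(1/56 + 1/28) = 0.2315; 0.79/0.2315 = 3.413; Φ(3.413 − 1.96) = 92.7% (exact t: 92.1%), against 92.9% stated. This reproduces. The plan gives no operating figure for the VO2peak regression.

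**Step 2. Exercise does nothing to the outcome.** Let V be VO2peak change and Y outcome change, both in within-arm SD units. With 2:1 allocation the variance of the arm indicator is (2/3)(1/3) = 2/9. So Var(V) = 1 + 2g²/9, and the correlation between V and Y without arm has size

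r / √(1 + 2g²/9).

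At g = 1 this is r/1.1055. By Fisher's z, the chance of significance is about Φ(atanh(corr) × √81 − 1.96), plus a negligible opposite tail.

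| r | Correlation without arm | Closed form | Simulation, slope without arm | Randomised t-test |
|---|---|---|---|---|
| 0 | 0 | 5% | 5% | 5% |
| 0.1 | 0.090 | 13% | 13% | 5% |
| 0.2 | 0.181 | 38% | 38% | 5% |
| 0.3 | 0.271 | 71% | 71–72% | 5% |

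Over g = 0.65 to 1.3 the simulated rates are 12–14%, 34–42% and 66–76% for r = 0.1, 0.2 and 0.3. If 15% is lost from the current target of 120, leaving 102 (68 versus 34), they are about 15%, 44% and 79% at g = 1.

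**Step 3. Exercise works, but wholly outside fitness (d = 0.79, r = 0).** The correlation without arm is

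(2/9)·d·g / √[(1 + 2g²/9)(1 + 2d²/9)].

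- g = 0.65: 0.1141/√(1.0939 × 1.1387) = 0.102, significant in 15% of trials.
- g = 1.3: 0.2282/√(1.3756 × 1.1387) = 0.182, significant in 38% (simulation 39%).

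With arm in the model the slope is significant in 5%. Here no confounding is assumed, and the error comes only from omitting arm.

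**Step 4. Does keeping arm cure Step 2?** With arm in the model the partial correlation is r itself, so the chance is about Φ(atanh(r) × √80 − 1.96): 15%, 44% and 79% for r = 0.1, 0.2 and 0.3. Also requiring a significant arm effect on VO2peak, which is a joint test of the indirect path, gives 14%, 44% and 79% by simulation at g = 1. So it does not.

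**The case against.** **The analysis is secondary.** This stands. The randomised t-test is primary, non-primary analyses are to be labelled secondary, and regressing outcome change on fitness change is acceptable as an association. But a secondary label governs prominence and multiplicity. It does not make a mediation reading valid, and the plan states that reading with no later qualification.

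**The inflation rests on an assumed correlation.** This also stands. At r = 0 the Step 2 test holds 5%. The fitness-change evidence in the documents concerns atrophy, not amyloid, so it makes a non-zero r plausible without giving its size for SUVR. Step 3, however, needs no such correlation.

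**Stronger readings that the documents do not support.** A reader might infer that putting arm back restores a 5% error rate, since the randomised test stays there. It does not: Step 4 shows similar or slightly higher rates under shared causes. Baseline covariates cannot capture illness or test effort arising during the 52 weeks.

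A reader might also infer that the regression is confined to adherent participants. One paragraph of Statistical Analyses for Aim 1 calls it per protocol, while the paragraph that introduces it gives no adherence restriction. Selection on adherence is therefore possible but not established. If the 80%-of-sessions rule did apply, controls, who have no sessions, would have no evident counterpart.

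**Conclusion.** The mediation sentence claims more than the model can deliver. Under a zero exercise effect the slope is significant in about 13%, 38% and 72% of trials at 56 versus 28, for assumed within-arm correlations of 0.1, 0.2 and 0.3 and an arm gap of 1 SD. If the benefit runs wholly outside fitness, it is significant in about 15% to 39% of trials, against 5% with arm included. These are conditional figures, not predictions for this trial.

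The same limit applies where Aim 3 reuses the continuous measure. A reader might conclude that the trial's main result is compromised, but the primary randomised comparisons do not use this model and are unaffected. This is a minor to moderate correction to a secondary analysis.

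**What to change.** 1. Delete the sentence saying that the regression assesses mediation. Describe the VO2peak regression as an exploratory, non-randomised association, and carry the same description to the continuous measure in Aim 3.
2. State whether it uses all randomised participants with data or an adherence-defined set, and reconcile the two paragraphs of Statistical Analyses for Aim 1.
3. If mediation is to be examined, keep arm in the model and estimate the indirect effect from arm through VO2peak change to outcome change, with a confidence interval. Adjust for baseline VO2peak, baseline outcome, age, sex and amyloid group. Add a sensitivity analysis showing how strong an unmeasured shared cause would have to be to account for the estimate, and do not present the result as proof of mechanism.

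Items 1 and 2 cost only wording. Item 3 costs one further model and its sensitivity analysis. It removes the error from effects outside fitness, but the estimate will be less precise and remains open to confounding.

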Quality Assurance for Training and Data Collection: While a site is active, a member of the exercise intervention team makes site visits regularly to collect data forms, review quality of data collection (e.g., completeness and accuracy of data entry) and ensure competency in the standard application of the exercise protocol through observations of the exercise instructors. If procedural discrepancies are identified, these are then addressed with the instructors.

Safety: One trainer supervises a maximum of four participants at one time. If the participant is deemed a fall risk, the trainers are prepared to provide 1:1 supervisor to participant supervision. All of the treadmills are equipped with handrails and emergency stop switches. All of the trainers are Adult CPR certified and trained in the use of portable defibrillators which are available at all of the facilities.

Control Group

Standard-of-care education (SOC) – All study participants randomized to the control group will receive education from study staff about the importance of maintaining a healthy and active lifestyle. Each enrollee will receive our SOC education based on a standardized script along with standardized literature, “Exercise and Physical Activity: Your Everyday Guide from the National Institutes on Aging” and the “KUADC Promoting Healthy Brain Aging.” These booklets provide vetted and reliable information for older adults on how to exercise. Participants may ask questions of study staff at that time. Participants randomized to the control group will receive no further counseling on physical activity.

Aim 1: Determine the effect of aerobic exercise on amyloid burden in individuals with preclinical AD (cognitively normal with elevated cerebral amyloid) and those without elevated amyloid.

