Rationale: Amyloid imaging has promise as a potential biomarker for identifying the preclinical stages of AD and is being used as an outcome measure to assess biological effects of therapies in clinical trials. This study uses amyloid imaging to 1) identify individuals with early AD pathophysiologic changes (preclinical AD) who are likely at higher risk of developing AD, and 2) to assess potential disease-modifying effects of exercise on early AD pathophysiology. Amyloid imaging techniques have demonstrated sensitivity to change in response to therapeutic agents (Bapineuzumab, see power analyses below).¹¹⁹ Additionally, amyloid burden increases longitudinally in nondemented older adults, with the greatest increase observed in individuals who are amyloid elevated at baseline (i.e., similar to our preclinical AD cohort).¹²⁰ As animal studies¹⁵⁻¹⁷ and indirect human data^{97, 98} suggests exercise modifies the AD pathophysiologic cascade, we hypothesize that aerobic exercise will be associated with reduced cortical amyloid burden over 52 weeks compared to controls.

Preliminary Experience: We have performed 21 Florbetapir PET scans through several clinical trials (ADNI, IGIV, Bapineuzumab). Our nondemented sample (n=10, mean age 82) had 4 of 10 individuals with an amyloid burden similar to that seen in our AD sample (n=11, mean age 76), 10 of 11 whom demonstrated elevated amyloid burden (Figure 2).

Data Acquisition: Florbetapir PET imaging will be obtained at screening and after 52 weeks of exercise (+/- 1 week). Subjects will have a catheter placed for IV administration of Florbetapir F 18 Injection. Vital signs will be taken in a supine position immediately prior to administration of Florbetapir (within 5 minutes). Subjects will receive a single IV bolus of Florbetapir (370 MBq) followed by brain PET imaging of 10 minutes duration, approximately 50 minutes post-dose injection. Adverse events will be continuously monitored during the imaging session and a participant will have follow-up phone call within 2 business days after the imaging session to confirm patient well-being and to collect information about any new adverse events.

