Rationale: Magnetic resonance (MR) based volumetric studies are increasingly used as surrogate outcome measures of disease¹²¹ to more efficiently demonstrate an intervention's disease-modifying effect. Our primary focus will be on the effect of exercise in modifying regional atrophy in the hippocampus with secondary outcome measures including rates of whole-brain and precuneal atrophy. The hippocampus is an important structure in mediating memory processes¹²² and is among the earliest affected regions in AD.¹²³ Additionally, atrophy of the hippocampus has been observed in preclinical AD and is associated with asymptomatic cerebral amyloid deposition.^{48, 59} We are also interested in the effect of exercise on regional atrophy in the precuneus, an important node in the default mode network that, along with the hippocampus, appears to be vulnerable to structural and functional decline associated with asymptomatic cerebral amyloidosis.^{61, 124-128} Importantly, these structures may be responsive to exercise: a randomized controlled trial of 52 weeks of exercise attenuated hippocampal atrophy⁷⁷ while physical activity levels are associated with hippocampal and precuneus volumes in nondemented older adults.¹²⁹

Preliminary Experience: Our studies suggest that aerobic fitness (VO_{2peak}) in the earliest stages of AD is associated with whole brain atrophy⁷⁸ and atrophy in the hippocampus⁷⁹ while decline in aerobic fitness over 2 years is associated with greater atrophy in the parahippocampus.⁷⁴ Although our imaging data is limited to aerobic fitness measures (rather than an exercise intervention), the data suggest that exercise to maintain or enhance aerobic fitness may have disease modifying effects on AD-related structural changes. Additionally, our imaging methods are sensitive to hippocampal and precuneus atrophy as we observed annualized rates of atrophy in the hippocampus (1.72% [2.7]) and precuneus (0.56% [0.40]) in nondemented older adults (n=63) over two years. We expect to see greater rates of atrophy in our preclinical AD participants which will enhance our power to observe exercise-related effects.

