Statistical Analyses for Aim 2: We hypothesize that aerobic exercise will attenuate atrophy in the precuneus and hippocampus, two regions consistently identified with atrophy in preclinical AD and the earliest stages of AD. Volume measures of the hippocampus, precuneus, and of the whole brain (continuous variables) will be collected at baseline and 52 weeks. The primary measure of brain atrophy will be hippocampal volume.

The primary intent-to-treat analysis for atrophy will compare the change from baseline to 52 weeks between our two treatment groups. The two-sample t-test of the observed changes will be used for this comparison. Similar models will be generated for precuneus volume and whole brain volume, and for the per-protocol analyses described above. Given a single primary measure for this aim, no multiplicity adjustment will be made and secondary endpoints will be clearly indicated as such in resulting manuscripts. Model assessment and alternative approaches will follow as described in Aim 1.

Aim 3: Determine the effects of aerobic exercise on cognition in individuals with preclinical AD and those without elevated amyloid.

Rationale: Substantial evidence, including our own (see background above), exists demonstrating that aerobic exercise has a preferential effect on cognition, particularly in executive functioning.^{69, 70, 135} Thus, our primary outcome measure is executive function. This study, however, extends previous exercise-cognition studies as it seeks to provide evidence of a specific effect on AD pathophysiology (i.e., disease modifying effect) of aerobic exercise on AD-related pathophysiological change in preclinical AD. Thus, we will also assess key cognitive domains that are associated with asymptomatic cerebral amyloid deposition.

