CSF and imaging studies indicate that declines in global cognitive ability¹³⁶ and episodic memory (verbal-based,⁵⁰ visuospatial-based,^{137, 138} or both¹³⁹⁻¹⁴¹) are associated with the presence of cerebral amyloid. Thus, secondary outcomes include verbal and visuospatial-based episodic memory measures where we expect decline on these measures will be associated with higher amyloid deposition. Visuospatial ability is an excellent marker of preclinical AD (leading diagnosis by at least 3-years)¹⁴²⁻¹⁴⁵ and was the strongest cognitive indicator for PIB-positive status in a longitudinal study on healthy aging. Visuospatial ability is also strong indicator of executive functioning ability.¹⁴⁶ Although studies of the cognitive effects of aerobic exercise have not resulted in major improvements in episodic memory, no studies have assessed the cognitive effects of exercise in a cohort of individuals with preclinical AD who have expected accelerated rates of decline in episodic memory. By selecting amyloid elevated individuals, we are targeting individuals with preclinical AD who may benefit most from potential disease-modifying effects of aerobic exercise on AD pathophysiology. Thus secondary outcomes include verbal and visuospatial-based episodic memory measures, where we expect decline on these measures will be associated with higher amyloid deposition.

Additionally, three reports indicate cognitive decline in preclinical AD may be mediated by structural changes in the hippocampus^{136, 139, 140} and the concept of preclinical AD posits that hippocampal atrophy is a downstream effect of amyloid deposition. Moreover, this mediation hypothesis may explain a recent finding from Kraemer and colleagues¹⁴⁷ where better visual memory performance was associated with less hippocampal atrophy in exercising nondemented older adults.¹³⁹ Thus, we will test the mediation effect of hippocampal atrophy on the relationship between exercise and cognitive decline over 52-weeks across all 3 outcomes. We anticipate visual memory to be the strongest of the multiple indicators.

Data Acquisition: All participants complete a 2- 3 hour neuropsychological test battery at baseline, 26-weeks, and 52-weeks. This battery includes selected tests with demonstrated responsiveness to aerobic exercise and sensitivity to change in preclinical AD. These tests will be aggregated into several domains: Executive Function, Visual Memory, and Verbal Memory, General Health, Emotional Health.

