Outcomes: Cognitive domains of Executive Function, Verbal Memory, and Visual Memory are face valid aggregates of related subtests that have generated moderate to large effect sizes across several reviews on cognition and aerobic exercise when aggregated. We have expertise using Confirmatory Factor Analysis (**CFA**) to determine the best fitting empirical model of data and create factor score weights that are sensitive indicators of cognitive change.^{157, 158} CFA is a common method used to aggregate true score (common) variance across multiple subtests and attenuate error. Thus, factor scores yield more reliable estimates of cognitive ability than individual tests because they are purer indices of ability.^{159, 160} This is desirable because cognitive performance in aging individuals is highly variable. Individual subtests are not as efficient as CFA-

based composite scores. We have shown in previous work^{142, 161} that longitudinal declines in cognitive ability can best be characterized with a model¹⁶² of specific mental abilities.

Statistical Analyses for Aim 3: This intent-to-treat analysis will use a two-sample t-test to compare change from baseline to 52 weeks between our treatment and control groups on the primary (executive function) and secondary outcomes (verbal and visual memory). Secondary endpoints will be clearly indicated as such in resulting manuscripts; therefore no further multiplicity adjustments will be made. Because cognition is measured at three time points (baseline, 26-, and 52-weeks), linear mixed models will also provide additional information such as to the functional form of the potential benefits of exercise (e.g., linear increasing benefit over time, initial benefit within 26 weeks that is sustained, etc.). Assessments of these linear mixed models will be conducted by evaluating model assumptions through residual analyses (similar to that described above).

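### Aims 1 to 3 each name two amyloid groups, but no planned analysis estimates the exercise effect within either group or compares the two

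*Combined protocol and SAP*

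**What the plan says.** The Specific Aims and the heading of each aim's own section name both populations. Aim 1, for example, concerns "individuals with preclinical AD (cognitively normal with elevated cerebral amyloid) and those without elevated amyloid". Study Procedures plans 70 participants with preclinical AD and 50 with non-elevated amyloid, allocated 2:1 to exercise or control.

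The rationale sections treat the elevated group as different:
- Aim 1, Rationale: amyloid rises over time in nondemented older adults, "with the greatest increase observed in individuals who are amyloid elevated at baseline".
- Aim 2, Preliminary Experience: "We expect to see greater rates of atrophy in our preclinical AD participants".
- Aim 3, Rationale: selecting amyloid-elevated people is described as "targeting individuals with preclinical AD who may benefit most from potential disease-modifying effects of aerobic exercise on AD pathophysiology".

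The primary analyses compare the arms over everyone:
- Aim 1: the analysis "will compare the change from baseline to 52 weeks between our two treatment groups using the two-sample t-test".
- Aim 2: "The two-sample t-test of the observed changes will be used for this comparison".
- Aim 3: "This intent-to-treat analysis will use a two-sample t-test to compare change from baseline to 52 weeks between our treatment and control groups".

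The other planned analyses are the six regional ratios, a per-protocol set, regression on change in VO2peak, mixed models for cognition, mediation by hippocampal atrophy, and exploratory t-tests and regressions. The mixed models are there because "linear mixed models will also provide additional information such as to the functional form of the potential benefits of exercise". The mediation text under Aim 3 refers to amyloid binding in relation to cognitive decline, which is not an exercise effect by amyloid group. Baseline enters only by subtraction in the change score. The Sample Size Justification says that further analyses will be reported as secondary, but lists none by amyloid group.

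**The concern.** The trial deliberately enrols two populations and writes both into every main aim, yet the plan yields one number per aim, averaged over a 70:50 mix. A null average could be read as no effect in preclinical AD, the population in the trial's title. A positive average could be read as benefit in both groups. Results by amyloid group will naturally be wanted. As the plan stands they would be post hoc, because labelling other analyses as secondary does not fix in advance which ones will be done.

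**Working it through.** **1. The plan's own power.** Inputs from the Sample Size Justification: 56 exercise and 28 control, two-sided alpha 0.05, d = 0.79 (Aim 1) and 0.66 (Aim 2). With noncentrality d / √(1/56 + 1/28), the noncentral t gives 92.1% and 80.5%; the normal approximation gives 92.7% and 81.4%. The plan states 92.9% and 81.4%, so its figures reproduce.

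**2. Numbers by group (assumption).** The power text starts from 100 enrolled, while the current plan enrols 120. With 15% dropout, 120 × 0.85 = 102 completers, or 68:34. Elevated: 70 × 0.85 = 59.5, about 40:20. Non-elevated: 50 × 0.85 = 42.5, about 28:14. This takes dropout and the 2:1 ratio to be the same in both groups.

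**3. What the average test sees.** Let f be the non-elevated effect as a share of the elevated effect, with a common SD. The average effect is d × (70/120 + f × 50/120). For d = 0.79 and f = 0 this is 0.79 × 0.583 = 0.46.

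| f | Average effect, Aim 1 | Power, 68:34, d = 0.79 | Power, 56:28, d = 0.79 | Power, 68:34, d = 0.66 |
|---|---|---|---|---|
| 0% | 0.46 | 58% | 50% | 44% |
| 25% | 0.54 | 73% | 64% | 57% |
| 50% | 0.63 | 84% | 76% | 69% |
| 75% | 0.71 | 92% | 86% | 80% |
| 100% | 0.79 | 96% | 92% | 88% |

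The elevated group alone (40:20) has 81% power at d = 0.79 and 66% at d = 0.66. The all-participant test overtakes it once f exceeds about 43%, for either effect size. For Aim 3 at the stated d = 2.32, the average effect at f = 0 is 2.32 × 0.583 = 1.35 and power is still above 99.9%, so dilution costs no power there.

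**4. What by-group estimates could deliver.** 95% half-widths in SD units:
- Elevated: 2.00 × √(1/40 + 1/20) = 0.55.
- Non-elevated: 2.02 × √(1/28 + 1/14) = 0.66.
- Difference between groups: standard error √(1/40 + 1/20 + 1/28 + 1/14) = 0.427, and 1.98 × 0.427 = 0.85.

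Power to detect that difference is 45 / 28 / 15% when f is 0 / 25 / 50% of 0.79.

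**5. Covariates.**
- *Amyloid status.* If the groups differ in mean change by D SD, leaving status out inflates the variance by 1 + (70/120)(50/120)D², which is 1.015 at D = 0.25 and 1.061 at D = 0.5. At 68:34 the power regained is 0.2 and 1.0 point for d = 0.79, and 0.5 and 2.0 points for d = 0.66. These figures assume an equal effect in both groups. In simulations of 10,000 trials per setting, with D = 0.5, d = 0.79 and f from 0 to 100%, power moved from 58.3 / 71.7 / 82.9 / 90.7 / 94.6% without status to 58.1 / 71.3 / 83.3 / 91.4 / 95.7% with it.
- *Aim 2 on the documents' figures.* With the assumed correlation of 0.95, the change SDs are √(0.74² + 0.69² − 2 × 0.95 × 0.74 × 0.69) = 0.231 and √(2 × 0.80² × 0.05) = 0.253, pooled 0.242. Then 0.16 / 0.242 = 0.66, as stated, and 0.242 / 4.895 = 4.95% of volume. Suppose that the 1.72% annual hippocampal atrophy under Aim 2 is the non-elevated rate, and the elevated rate is 1.5 or 2 times it. That sample is not described as amyloid-classified, so this is an assumption. The group difference is 0.86% or 1.72%. On an SD of 4.95%, D is 0.17 or 0.35 and the gain 0.2 or 0.9 point. If the bracketed 2.7 beside the rate is an SD, D is 0.32 or 0.64 and the gain 0.8 or 3.2 points.
- *Baseline, Aim 2.* With equal variances, the ratio of adjusted to change-score variance is (1 + ρ)/2. At ρ = 0.95 power goes from 87.5% to 88.3%; at ρ = 0.99, from 87.5% to 87.7%.

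**The case against.** Each aim can be read as a single hypothesis about the combined sample, and randomisation makes the t-test valid for it. The Non-elevated Amyloid Group section restricts that group to a mean SUVR of at least 1.0 because it may be enriched with people who accumulate amyloid. This supports a combined estimate and argues against the 0% row of the table. The funding mechanism is for pilot trials, and by-group estimates will be imprecise: the half-width for the difference, 0.85 SD, exceeds the whole assumed effect of 0.79. All of this stands. It argues for labelling by-group results as estimates, not for leaving them unplanned.

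A reader might infer that the protocol predicts a different response to exercise in the two groups. The Aim 1 and Aim 2 passages concern rates of amyloid accumulation and atrophy. Only the Aim 3 rationale touches benefit, as a possibility, and in justifying the choice of population. A reader might also infer that the plan ignores the groups altogether. The aim headings and the eligibility criteria name them, and the mediation text uses amyloid binding; the gap is in the planned analyses of exercise effect.

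The case for changing the primary model on grounds of precision is weak. The gains are small and, when the effect differs by group, not consistent. In Aim 1 amyloid status and baseline SUVR also overlap, since both come from amyloid PET.

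**Conclusion.** The point holds as a gap between the aims and the planned analyses. The plan would report whether exercise works on average, but nothing prespecified would say in which of its two named groups. It does not follow that the primary t-test is biased or the wrong test. Nor does it follow that combining the groups generally costs power: the combined test beats the elevated-group estimate when the non-elevated effect is above about 43% of the elevated one. Power at d = 0.79 runs from 58% to 96% over the range of f, against 81% for the elevated group alone.

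The documents give no effect or SD by amyloid group. These figures therefore rest on 120 enrolled, 15% dropout and 2:1 allocation in each group, a common SD, and the plan's effect sizes applied to the elevated group. The covariate gain is minor: about 0.2 to 2 points for an assumed group difference of 0.25 to 0.5 SD, and under 1 point from baseline in Aim 2.

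**What to change.** Amend the analysis text for Aims 1 to 3, dated before any look at outcomes by arm:

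- Prespecify as secondary the arm effect within each amyloid group, and the difference between those effects from an arm-by-amyloid term, each with a 95% confidence interval. Define the groups by the majority VisQ read of the screening scan.
- State that these are estimates with limited power, and that an interval including zero will not be read as absence of effect.
- As a free improvement, include the baseline value of the outcome and amyloid status as covariates in the comparison of 52-week change by arm, report the unadjusted t-test alongside, and say in advance which of the two is primary.

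The first two items meet the main point even if the t-test stays primary. The cost is wording: amyloid status and baseline outcomes are already part of the planned data collection, and no participants, visits or scans are added.
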